11.3 EXPAND NON-CONSTANT VARIANCE MODEL

The model developed in section 9.2 will be expanded to include relevant demographic and baseline characteristics as determined by exploratory data analysis on those features. The model will also be modified to try and include the Composite Scores so that the influence of each Composite Score's difference on the overall difference can be seen/fit simultaneously. Hierarchical modelling will be used here to pool information across relevant demographic/baseline/composite score groups. This model will be used to predict an individual's likelihood and uncertainty to be classified in the same Linus Score Categorization (In range, Indeterminate, Out of Range) as a function of the average score of the two assessments.

The Evaluable Population will be used for these analyses.

A table will summarize Score Differences (both credible and prediction interval differences) across relevant baseline/demographic groups.

A second table will summarize score differences (both credible and prediction interval differences) for the overall and Composite Scores based on the above model.

A figure will summarize the likelihood of a participant to be classified in the same Linus Score Categorization (y-axis) across a range (0 - 100) of score averages (x-axis). The mean line, 96% credible intervals around that mean line, and 96% prediction intervals around that mean line will all be plotted on the same figure.

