4 SAMPLE SIZE

The primary null and alternative hypotheses are:

$$H_0: LCI_{LLoA} \leq -\delta \text{ or } UCI_{ULoA} \geq \delta$$

$$H_1: -\delta < LCI_{LLoA} < UCI_{ULoA} < \delta$$

where $\delta = 30$ is the pre-specified maximum allowable difference, LCI_{LLoA} is the lower bound of the two-sided 95% confidence interval (CI) for the lower bound of the two-sided 95% limits of agreement (LoA), UCI_{ULoA} is the upper bound of the two-sided 95% CI for the upper bound of the two-sided 95% LoA.

The primary endpoint will be analyzed using Bland-Altman method. This study will produce LoA and associated CIs from the two measurements on each subject (further details are below). The conclusion that the two measurements are in agreement (i.e. equivalent) depends on whether the CIs constructed from the data are within the boundaries set from the maximum allowable difference. An evaluable sample size of 41 subjects achieves at least 90% power to detect agreement when the confidence level of the LoA is 95%, the confidence level of the CIs about the LoA is 95%, and the maximum allowable difference is 30 ($\delta = 30$). The mean and standard deviation of the sample differences are anticipated to be 10 and 7, respectively.

Accordingly, approximately 175 subjects will be enrolled in order to obtain a DCTclock-tablet training dataset of at least 100 subjects and a DCTclock-tablet validation dataset of greater than 41 evaluable subjects.

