9.2 NON-CONSTANT VARIANCE & ASSESSMENT OF SITE HOMOGENEITY

A generative model will be fit of the following form:

$$\begin{aligned} \text{Score Difference} &\sim N(\mu, \sigma) \\ \mu &= \alpha\mu + \beta_1 * \text{Location} + \beta_2 * \text{Test Order} \\ \sigma &= k * \exp(\alpha\sigma + \beta_3 * \text{Average Score}_2 + \beta_4 * \text{Average Score}) \end{aligned}$$

- ‘Location’ and ‘Test Order’ will be one hot encoded indicator variables for the trial location site and order in which the test was given (ie. DCTclock pen assessment first or DCTclock tablet assessment first) respectively.
- Average Score will be calculated as: $(\text{DCTclock pen score} + \text{DCTclock tablet score}) / 2$
- Score Difference will be calculated as: $(\text{DCTclock tablet score} - \text{DCTclock pen score})$
- The parameters k , $\alpha\mu$, and $\alpha\sigma$ are constants

This model will permit the disentangling of site specific impacts and the rate of learning improvement between the first and second assessments while also allowing the variance in score difference to vary as a function of the average score.

The Evaluable Population will be used for this analysis.

Two tables will summarize this model. The first will include the mean estimated coefficient values along with their 96% credible intervals. The second will breakdown the estimated differences in average Score Difference between the site locations and the order in which the assessments were completed. This table will include the mean differences as well as the max 96% prediction interval ranges for each combination of site and order.

A figure will display the 96% prediction intervals for Score Difference (y-axis) as a function Average Score (x-axis) over the range 0 - 100 generated from the fit model above. The Evaluable Population will be plotted over this interval for a visual assessment of the model fit. The max 96% prediction interval range will be added to the figure.

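### SAP 11.3 plots same-category agreement against the average of the pen and tablet scores, so the curve falls to zero at every category boundary by construction and cannot show the direction of category change

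*SAP*

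**What the plan says.** SAP 11.3, under Other Planned Analyses, builds on the difference model: "The model developed in section 9.2 will be expanded to include relevant demographic and baseline characteristics". The expanded model is then used to predict whether a person is "classified in the same Linus Score Categorization (In range, Indeterminate, Out of Range) as a function of the average score of the two assessments". The accompanying figure puts that likelihood on the vertical axis, "across a range (0 - 100) of score averages (x-axis"), with 96% credible and prediction intervals.

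SAP 9.2 supplies the definitions. The average is half the sum of the pen and tablet scores. The difference is tablet minus pen and is normally distributed, with a mean that depends on site and test order and a spread that depends on the average.

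Neither document gives the category cut-offs. The SAP plans no cross-table of pen category against tablet category and no count of people who move up or down a category, either in the text or in the Appendix A shells as far as they can be read.

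**The concern.** The primary endpoint is equivalence in assessing cognitive impairment, and Protocol 6.3 intends the tablet for clinicians evaluating cognitive function. The primary criterion allows differences of up to 30 points on a score that SAP 9.2 plots over 0 to 100. Meeting it does not by itself show that people keep their category. SAP 11.3 is the only place that asks this.

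The chosen horizontal axis causes two problems. Near a cut-off, the average can only sit there if the two scores straddle it or tie, so low agreement is guaranteed whatever the devices do. A reader of the figure could blame the tablet for a dip that pen against pen would also produce. And because the average treats the two scores alike, a tablet that moves people up a category looks the same as one that moves them down. In practice a clinician has one score, not the average of two.

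**Working it through.** **Inputs.** A = (pen + tablet)/2 and D = tablet − pen (SAP 9.2). Planning values (SAP 4): "The mean and standard deviation of the sample differences are anticipated to be 10 and 7, respectively". The sign of the 10 is not stated, so both signs are used. No cut-offs are given, so results are expressed as distance h from the nearest one.

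**The plan's own figure.** SAP 11.3 states no number. The planning values come from the sample-size statement "An evaluable sample size of 41 subjects achieves at least 90% power to detect agreement", which can be checked. With a noncentral-t formula, SE = 7·√(1/41 + 1.96²/80) = 1.884. The noncentrality values are (30 − 10 − 13.72)/1.884 = 3.33 and (30 + 10 − 13.72)/1.884 = 13.95. Power is 0.902, and 41 is the smallest n reaching 90%. (Simulating the exact confidence-interval rule of SAP 9.1 at n = 41 gives 0.875; this does not bear on the present point.)

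**Step 1: recover the two scores.** pen = A − D/2 and tablet = A + D/2. Each lies |D|/2 from A, on opposite sides.

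**Step 2: condition for the same category.** The nearest cut-off is crossed first, so with three categories the scores share one only if |D|/2 < h. Hence

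P(same | A) = P(−2h < D < 2h) = Φ((2h − m)/s) − Φ((−2h − m)/s), where m and s are the mean and SD of D.

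**Step 3: two consequences.** At h = 0 the expression is zero for every m and s, so adding covariates to the model cannot remove the dip. Replacing m by −m leaves it unchanged.

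**Step 4: numbers with s = 7.**

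| h (points) | m = 0 | m = +10 | m = −10 |
|---|---|---|---|
| 0 | 0 | 0 | 0 |
| 1 | 0.225 | 0.083 | 0.083 |
| 3 | 0.609 | 0.273 | 0.273 |
| 5 | 0.847 | 0.498 | 0.498 |
| 10 | 0.996 | 0.923 | 0.923 |

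For example, h = 5 and m = 10 gives Φ(0) − Φ(−20/7) = 0.500 − 0.002 = 0.498. Even with s = 3 and no shift, agreement at h = 1 is only 0.495, and at h = 0 it is still zero. Simulation of 2,000,000 pairs at three assumed cut-off pairs gave agreement of 0.001 to 0.008 within 0.05 points of a cut-off.

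**Step 5: what the curve cannot show (illustration).** Assume cut-offs of 40 and 60, averages uniform on 0 to 100, and s = 7. A shift of +10 puts 20.3% of people in a higher category on the tablet and 0.5% in a lower one. A shift of −10 gives 0.5% higher and 20.2% lower. Same-category agreement is 79.3% in both cases.

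**Step 6: conditioning on the pen score (illustration).** Take one cut-off and assume D independent of the pen score. For a pen score h above the cut-off, P(tablet also above) = Φ((h + m)/7). At h = 0 and m = 0 this is 0.50. At h = 5 it is 0.984 for m = +10 and 0.238 for m = −10. The boundary zero disappears and direction becomes visible.

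These values depend on the assumption. If D is instead independent of A, then cov(D, pen) = −49/2 = −24.5. With A assumed normal with mean 50 and SD 10 to 25, and a cut-off from 40 to 75, the 0.50 ranges from 0.20 to 0.63, the 0.984 from 0.87 to 0.99, and the 0.238 from 0.06 to 0.33. The contrast survives, but the exact percentages do not.

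**The case against.** The strongest reply is that the average is the natural axis in a Bland-Altman framework. SAP 9.1 plots against it, the 9.2 variance model conditions on it, and neither score is error-free, so conditioning on one brings in regression to the mean. That justifies the average for differences. It does not rescue the category curve, whose boundary zeros follow from the axis alone.

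A reader might infer that the SAP conceals whether the tablet reads high or low. It does not. Signed differences are tabulated under SAP 9.1 and 9.3 (though 9.1 states pen minus tablet, and 9.2 and 9.3 tablet minus pen). The 9.2 model estimates the mean difference by site and order, 9.3 adds a scatter plot with the line of identity and a Deming regression, and 11.3 has its own difference tables. Only the direction of category change is missing.

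A reader might also infer that bringing composite scores into the model, so that their influence on the "difference on the overall difference can be seen/fit simultaneously", overstates category agreement. That would follow only if composite differences were held fixed in the prediction. SAP 11.3 does not say so, and the figure's axis is the score average alone.

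Two further limits stand. Exact zero requires continuous scores. If scores are whole numbers, which is not stated, tied pairs agree at a boundary: about 2% for a mean shift of 10 and 6% for none, at SD 7. And the analysis is exploratory, with no test or success rule attached.

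**Conclusion.** The concern holds for the same-category prediction in SAP 11.3 and its figure. Given the SAP's own definitions, the dip to zero at each boundary and the insensitivity to the sign of the shift are algebraic and need no assumption about cut-offs. The size of the dip away from the boundary rests on normal differences and the planning SD of 7: 0.225 at 1 point and 0.847 at 5 points with no shift, and 0.498 at 5 points with a shift of 10 either way. The reclassification and pen-conditional percentages are illustrations only, because the documents give neither cut-offs nor a score distribution.

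The primary test, the sample size and the safety analysis are unaffected. The point is worth acting on because no other planned output compares pen and tablet categories.

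**What to change.** In SAP 11.3:

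1. Add a 3×3 table of pen category by tablet category, with the proportions moved up and moved down, by test order and overall.
2. Make the main prediction plot the probability of each tablet category, and of the same category, given the DCTclock-pen score. Obtain it from the fitted difference model together with an estimated distribution of the average, or from a joint model or a regression of tablet on pen.
3. Keep the average-based curve only as a supplement, with a note that its zeros at the boundaries are built in.

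No new data are needed. The cost is more than relabelling an axis: the 9.2 model describes the difference given the average, so a prediction given the pen score needs the extra distribution or a different model. Because the pen score is measured with error, the new curve describes agreement with a single pen result and includes regression to the mean; the SAP should say so beside the figure.

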12 SUMMARY OF CHANGES FROM THE PROTOCOL

The following table provides a list of changes from the protocol to the SAP, and the justification for each change.

Section	Description	Justification
7.1 Analysis Software	Added SAS® Software version 9.4 or later (the protocol only specifies R version 3.6 or later)	This will allow for programmers to use either SAS or R for analyses

13 REPORTING CONVENTIONS

All reporting will meet the standards of SOP-68 AS Data Analysis Reporting and SOP-83 AS Programming Standards.

14 APPENDIX A: TABLE, LISTING AND FIGURE SHELLS

	Table # Subject Accountability		
	Group 1 DCTclock-pen First	Group 2 DCTclock-tablet First	Total
Screened N			
Eligible N			
ITT N			
Visit 1 [% (n/ITT N)]			
Visit 2 [% (n/ITT N)]			
Evaluable N			
Visit 1 [% (n/Evaluable N)]			
Visit 2 [% (n/Evaluable N)]			
Validation N			
Visit 1 [% (n/Validation N)]			
Visit 2 [% (n/Validation N)]			
Training N			
Visit 1 [% (n/Training N)]			
Visit 2 [% (n/Training N)]			
Safety N			
Visit 1 [% (n/Safety N)]			
Visit 2 [% (n/Safety N)]			

	Table # Withdrawals ITT Population	Group 1 DCT Clock-pen First N =	Group 2 DCT clock-tablet First N =	Total N =
All Withdrawals % (n/ITT N)				
Timing of withdrawal % (n/ITT N)				
During first visit				
After first visit but before second visit				
During second visit				
Reason for withdrawal % (n/ITT N)				
Subject did not want to complete this testing session				
Subject did not want to return for a second testing session				
Subject did not show up for scheduled testing session and could not be reached for rescheduling within the time window				
PI felt that it was not in the best interest of the subject to continue in the study				
Subject met exclusion criteria during visit 2				
None given				
Other				

Note: Percentages are based on the number of subjects in the ITT Population.

This table will be repeated for Evaluable Population

Table # Protocol Deviation ITT Population									
Randomization Group	Site	Subject ID	Validation Population	Protocol Deviation #	Date Type	Date of Deviation	Time of Occurrence	Reason for Deviation	Justification/Corrective Action
Group X	XXX	XXX-XXX	Y/N	XXXXXX	XX/XX/XXXX	XXXXXX	XXXXXXXXXX	XXXXXXXXXX	XXXXXXXXXX
					XX/XX/XXXX	XXXXXX	XXXXXXXXXX	XXXXXXXXXX	XXXXXXXXXX
					XX/XX/XXXX	XXXXXX	XXXXXXXXXX	XXXXXXXXXX	XXXXXXXXXX
	XXX	XXX-XXX	Y/N	XXXXXX	XX/XX/XXXX	XXXXXX	XXXXXXXXXX	XXXXXXXXXX	XXXXXXXXXX
					XX/XX/XXXX	XXXXXX	XXXXXXXXXX	XXXXXXXXXX	XXXXXXXXXX
									...

This listing will be ordered by randomization group, then site, then subject ID.

Table # Subject Demographics ITT Population			
	Group 1 DCTclock-pen First N =	Group 2 DCTclock-tablet First N =	Total N =
Age (yrs)			
Mean \pm SD (ITT N)			
Median (Min, Max)			
Gender % (n/ITT N)			
Male			
Female			
Other			
Unavailable			
Race % (n/ITT N)			
American Indian			
Alaskan Native			
Asian			
Black/African American			
Hispanic/Latino			
Native Hawaiian/Pacific Islander			
White/Caucasian			
Unavailable			
Ethnicity % (n/ITT N)			
Non-Hispanic/Latin			
Hispanic/Latin			
Unknown			
Unavailable			
Handedness % (n/ITT N)			
Right			
Left			
Am bi			
Am bi L>R			
Am bi R>L			
Unknown			
Unavailable			
Education % (n/ITT N)			
Mean \pm SD (ITT N)			
Median (Min, Max)			

Note: Percentages are based on the number of subjects in the ITT Population.

This table will be repeated for Evaluable Population

Table # Medications at Baseline ITT Population				
Randomization Group	Site	Subject ID	Validation Population	Medication Name
Group X	XXXX	XXX-XXX	Y/N	XXXXXXXXXXXX
			Y/N	XXXXXXXXXXXX
Group X	XXXX	XXX-XXX	Y/N	XXXXXXXXXXXX
				...

This listing will be ordered by randomization group, then site, then subject ID.

Table # Dementia Medications at Baseline ITT Population			
	Group 1 DCTclock-pen First N =	Group 2 DCTclock-tablet First N =	Total N =
Aricept (Donepezil) % (n/ITT N)			
Currently			
Previously			
Namenda (Memantine) % (n/ITT N)			
Currently			
Previously			
Axona % (n/ITT N)			
Currently			
Previously			
Exelon (Rivastigmine) % (n/ITT N)			
Currently			
Previously			
Razadyne (Galantamine) % (n/ITT N)			
Currently			
Previously			

This table will be repeated for Evaluable Population.

Table # MMSE Score at Baseline ITT Population			
	Group 1 DCTclock-pen First N =	Group 2 DCTclock-tablet First N =	Total N =
Orientation to time			
Mean ± SD (N)			
Median (Min, Max)			
Orientation to place			
Mean ± SD (N)			
Median (Min, Max)			
Registration			
Mean ± SD (N)			
Median (Min, Max)			
Attention and calculation (WORLD)			
Mean ± SD (N)			
Median (Min, Max)			
Recall			
Mean ± SD (N)			
Median (Min, Max)			
Naming			
Mean ± SD (N)			
Median (Min, Max)			
Repetition			
Mean ± SD (N)			
Median (Min, Max)			
Comprehension			
Mean ± SD (N)			
Median (Min, Max)			
Reading			
Mean ± SD (N)			
Median (Min, Max)			
Writing			
Mean ± SD (N)			
Median (Min, Max)			
Drawing			
Mean ± SD (N)			
Median (Min, Max)			
Total			
Mean ± SD (N)			
Median (Min, Max)			

This table will be repeated for **Evaluable Population**.

Table # Brief Neurological Exam at Baseline ITT Population			
	Group 1 DCTclock-pen First N =	Group 2 DCTclock-tablet First N =	Total N =
Had MRI in Past % (n/ITT N)			
Yes			
No			
MRI Results % (n/N with Past MRI)			
Stroke			
Large Bleed			
Punctate Bleed			
Atrophy			
Small Vessel Disease			
Mass/Tumor			
Amyloid Scan			
Amyloid CSF			
Uses Cane or Other Walking Aid % (n/ITT N)			
Yes			
No			
Lower Extremity Neurological Exam % (n/ITT N)			
Able to Perceive Monofilament % (n/N with Exam)			
Left foot % (n/N with Exam)			
Yes			
No			
Right foot % (n/N with Exam)			
Yes			
No			
Able to Perceive Vibration % (n/N with Exam)			
Left foot % (n/N with Exam)			
Yes			
No			
Right foot % (n/N with Exam)			
Yes			
No			

This table will be repeated for Evaluable Population.

Table # Hamilton-Veale Contrast Sensitivity Score at Baseline ITT Population			
	Group 1 DCTclock-pen First N =	Group 2 DCTclock-tablet First N =	Total N =
Left Score			
Mean ± SD (N)			
Median (Min, Max)			
Right Score			
Mean ± SD (N)			
Median (Min, Max)			
Binocular Score			
Mean ± SD (N)			
Median (Min, Max)			

This table will be repeated for **Evaluable Population**

Table # Purdue Peg Board Score at Baseline ITT Population			
	Group 1 DCTclock-pen First N =	Group 2 DCTclock-tablet First N =	Total N =
Left Score			
Mean \pm SD (N)			
Median (Min, Max)			
Right Score			
Mean \pm SD (N)			
Median (Min, Max)			
Binocular Score			
Mean \pm SD (N)			
Median (Min, Max)			

This table will be repeated for **Evaluable Population**.

Table # Medical History ITT Population			
	Group 1 DCTclock-pen First N =	Group 2 DCTclock-tablet First N =	Total N =
Parkinson's and related conditions % (n/ITT N)			
Currently			
Previously			
Sleep Apnea % (n/ITT N)			
Currently			
Previously			
Stroke or TIA % (n/ITT N)			
Currently			
Previously			
Liver or kidney disease % (n/ITT N)			
Currently			
Previously			
Tremor % (n/ITT N)			
Currently			
Previously			
Brain tumor % (n/ITT N)			
Currently			
Previously			
Psychiatric disorder (including anxiety or depression) % (n/ITT N)			
Currently			
Previously			
Dementia (any type) % (n/ITT N)			
Currently			
Previously			
Diabetes % (n/ITT N)			
Currently			
Previously			
Epilepsy % (n/ITT N)			
Currently			
Previously			
Mild cognitive impairment (MCI) % (n/ITT N)			
Currently			
Previously			
Multiple sclerosis % (n/ITT N)			
Currently			
Previously			
Traumatic brain injury (with loss or consciousness) % (n/ITT N)			
Currently			
Previously			
Total number of traumatic brain injuries (among those who had indicated previous traumatic brain injury)			
Mean \pm SD (N)			
Median (Min, Max)			

This table will be repeated for Evaluable Population.

Table # Primary Effectiveness Endpoint for DCTclock Overall Score Validation Population			
	Group 1 DCTclock-pen First N =	Group 2 DCTclock-tablet First N =	Total N =
DCTclock-pen			
Mean ± SD (N)			
Median (Min, Max)			
DCTclock-tablet			
Mean ± SD (N)			
Median (Min, Max)			
Difference (DCTclock-tablet – DCTclock-pen)			
Mean difference ± SD (CI)			
Median (Min, Max)			
p-value for Equivalence (Margins of +/- 30)			
Comparison			
Lower Limit of Agreement (CI)			
Upper Limit of Agreement (CI)			
RMSD			
ANOVA p-value			

Figure #
Primary Effectiveness Figure (Bland-Altman Plot)

[figure not shown]

Table # Primary Effectiveness Non-Constant Variance Model Summary Evaluable Population	
	Coefficient Value (96% Credible Interval)
Constants	
$\alpha\mu$	
$\alpha\sigma$	
k	
Betas	
β_1	
β_2	
β_3	
β_4	

Table # Score Differences of Sites/Assessment Order w/ Non-Constant Variance Model Evaluable Population	
	Mean Score Difference (96% Credible Interval)
Site 1	
Tablet Assessment First (n = X)	
Pen Assessment First (n = X)	
Site 2	
Tablet Assessment First (n = X)	
Pen Assessment First (n = X)	

Table #			
Homogeneity by Site for DCTclock Overall Score			
Evaluable Population			
	Site 1 N =	Site 2 N =	Total N =
DCTclock-pen			
Mean \pm SD (N)			
Median (Min, Max)			
DCTclock-tablet			
Mean \pm SD (N)			
Median (Min, Max)			
Difference (DCTclock-pen – DCTclock-tablet)			
Mean difference \pm SD (CI)			
Median (Min, Max)			
Comparison			
Lower Limit of Agreement (CI)			
Upper Limit of Agreement (CI)			

Figure #
Primary Effectiveness Figure for Non-Constant Variance Model

[figure not shown]
[figure not shown]

Table # Secondary Effectiveness Endpoints for DCT-clock Drawing Efficiency Evaluable Population			
	Group 1 DCTclock-pen First N =	Group 2 DCTclock-tablet First N =	Total N =
DCTclock-pen			
Mean ± SD (N)			
Median (Min, Max)			
DCTclock-tablet			
Mean ± SD (N)			
Median (Min, Max)			
Difference (DCTclock-pen – DCTclock-tablet)			
Mean difference ± SD (CI)			
Median (Min, Max)			
p-value for Equivalence (Margins of +/- 30)			
Comparison			
Lower Limit of Agreement (CI)			
Upper Limit of Agreement (CI)			
RMSD			

This table will be repeated for the other DCTclock composite scales (Information Processing, Simple and Complex motor, Spatial Reasoning)

Figure #
Secondary Effectiveness Figure for DCT-clock Drawing Efficiency Composite Scale

This figure will be repeated for the other DCTclock composite scales (information processing, simple and complex motor, spatial reasoning)

	Table # Treatment-Emergent Adverse Events Safety Population							
	Visit 1		Between Visits		Visit 2		Total	
	Number of Events	Number of Subjects with Event [% (n/N)]	Number of Events	Number of Subjects with Event [% (n/N)]	Number of Events	Number of Subjects with Event [% (n/N)]	Number of Events	Number of Subjects with Event [% (n/N)]
Any TEAE								
Severity*								
Mild								
Moderate								
Severe								
Resulted in Study Discontinuation								
Yes								
No								
SAE								
Yes								
No								
Led to Death								
Yes								
No								
Relationship**								
DCTclock-pen								
Not Related								
Related								
Possible								
Probable								
Definite								
DCTclock-tablet/drawing tests								
Not Related								
Related								
Possible								
Probable								
Definite								
Decision making/reaction time								
Not Related								
Related								
Possible								
Probable								
Definite								
Balance/walking								
Not Related								
Related								
Possible								
Probable								
Definite								
PHQ-9/Lifestyle questionnaire								
Not Related								
Related								
Possible								
Probable								
Definite								
Speech elicitation assessments								
Not Related								
Related								
Possible								
Probable								
Definite								

Eye tracking assessments								
Not Related								
Related								
Possible								
Probable								
Definite								
Other study assessments								
Not Related								
Related								
Possible								
Probable								
Definite								
Concomitant medication								
Intercurrent intervention/procedure								
Pre-existing condition/Underlying disease								
Intercurrent condition								
Incidental finding								
Unknown								
Other								

*If a subject has more than one TEAE the events/subject are placed in the most severe category experienced.

**If subject has more than one TEAE, the events/subject are placed into the most related category experienced.

Table #
Treatment Emergent Adverse Events
Safety Population

Randomization Group	Site	Subject ID	Description	Visit Number / Date of Visit	Date of AE Onset/ Study Day Number	Date Resolved / Number of Study Days from Start of AE	SAE	Resulted in Study Discontinuation	Outcome	Severity	Related To	Action Taken
Group XX	XX	XXX-XXX	XXXXXX	XXXXXX XX/XX/XXXX	XX/XX/XXXX	XX/XX/XXXX XX	Y/N	Y/N	XXXXXX	XXXXXX	XXXXXX	XXXX
		XXX-XXX	XXXXXX	XXXXXX XX/XX/XXXX	XX/XX/XXXX	XX/XX/XXXX XX	Y/N	Y/N	XXXXXX	XXXXXX	XXXXXX	XXXX
		XXX-XXX	XXXXXX	XXXXXX XX/XX/XXXX	XX/XX/XXXX	XX/XX/XXXX XX	Y/N	Y/N	XXXXXX	XXXXXX	XXXXXX	XXXX
Group XX	XX	XXX-XXX	XXXXXX	XXXXXX XX/XX/XXXX	XX/XX/XXXX	XX/XX/XXXX XX	Y/N	Y/N	XXXXXX	XXXXXX	XXXXXX	XXXX
		XXX-XXX	XXXXXX	XX/XX/XXXX	XX/XX/XXXX	XX/XX/XXXX XX	Y/N	Y/N	XXXXXX	XXXXXX	XXXXXX	XXXX
												...

*Only AEs that have the onset time of “during assessments” or “between assessment visits” are included in this listing

Any specified reasons for SAEs will be listing in the SAE column after ‘Y’

Any instance in which the AE is at least possibly related will be listed and in parentheses will be the exact noted relationship i.e. balance/walking (probable)

**In any instance in which the action taken requires a specification, the specification will be written in parentheses i.e. medication (Ativan)
This listing will be ordered by randomization group, then site, then subject ID.**

Table #
Device Observations
Safety Population

[figure not shown]
Randomization Group	Site	Subject ID	Description	Observation #	Date of Observation (Study Day of Observation)	Related to AE	Related to Linus Platform Device Components	Time Observation Occurred	Type of Observation	Action Taken to Address Observation/ Outcome
Group X	XXX	XXX-XXX XXXXX	XXXXXX	XXXXXX	XX/XX/XXXX (XX)	Y/N	XXXXXX	XXXXX: XXXXX	XXXXX	XXXXXX
		XXX-XXX XXXXX	XXXXXX	XXXXXX	XX/XX/XXXX (XX)	Y/N	XXXXXX	XXXXX: XXXXX	XXXXX	XXXXXX
		XXX-XXX XXXXX	XXXXXX	XXXXXX	XX/XX/XXXX (XX)	Y/N	XXXXXX	XXXXX: XXXXX	XXXXX	XXXXXX
Group X	XXX	XXX-XXX XXXXX	XXXXXX	XXXXXX	XX/XX/XXXX (XX)	Y/N	XXXXXX	XXXXX: XXXXX	XXXXX	XXXXXX
		XXX-XXX XXXXX	XXXXXX	XXXXXX	XX/XX/XXXX (XX)	Y/N	XXXXXX	XXXXX: XXXXX	XXXXX	XXXXXX

This listing will be ordered by randomization group, then site, then subject ID.

Table #			
Exploratory Analysis: MMSE, RBANS and Linus Individual Tests and Overall Score Descriptives			
Validation Population			
	Visit 1	Visit 2	Total
MMSE			
Mean ± SD (N)		N/A	
Median (Min, Max)		N/A	
RBANS			
Mean ± SD (N)			
Median (Min, Max)			
Linus Total Score			
Mean ± SD (N)			
Median (Min, Max)			
Linus Platform Drawing Test: Pre-test			
Mean ± SD (N)			
Median (Min, Max)			
Linus Platform Drawing Test: Pathfinding			
Mean ± SD (N)			
Median (Min, Max)			
Linus Platform Drawing Test: Symbol			
Mean ± SD (N)			
Median (Min, Max)			
Linus Platform Drawing Test: Connect			
Mean ± SD (N)			
Median (Min, Max)			
Linus Platform Drawing Test: Tracing			
Mean ± SD (N)			
Median (Min, Max)			
Linus Platform Decision Making and Reaction Time Test: Simple Reaction Time			
Mean ± SD (N)			
Median (Min, Max)			
Linus Platform Decision Making and Reaction Time Test: Procedural Reaction Time			
Mean ± SD (N)			
Median (Min, Max)			
Linus Platform Decision Making and Reaction Time Test: Go/No-Go			
Mean ± SD (N)			
Median (Min, Max)			
Linus Platform Decision Making and Reaction Time Test: PHQ-9			
Mean ± SD (N)			
Median (Min, Max)			
Linus Platform Speech Elicitation Tasks: Complex Picture Description			
Mean ± SD (N)			
Median (Min, Max)			
Linus Platform Speech Elicitation Tasks: Category Naming			
Mean ± SD (N)			
Median (Min, Max)			
Linus Platform Speech Elicitation Tasks: Object Recall			
Mean ± SD (N)			
Median (Min, Max)			
Linus Platform Speech Elicitation Tasks: Sentence Reading			
Mean ± SD (N)			
Median (Min, Max)			
Linus Platform Speech Elicitation Tasks: Sustained Phonation			
Mean ± SD (N)			
Median (Min, Max)			

Linus Platform Speech Elicitation Tasks: Diadochokinetic Rate			
Mean ± SD (N)			
Median (Min, Max)			
Linus Platform Speech Elicitation Tasks: Story Recall			
Mean ± SD (N)			
Median (Min, Max)			
Linus Platform Speech Elicitation Tasks: List Learning			
Mean ± SD (N)			
Median (Min, Max)			
Linus Platform Eye Tracking-Based Memory Assessments			
Mean ± SD (N)	N/A		
Median (Min, Max)	N/A		
Linus Platform Gait and Balance Assessment			
Mean ± SD (N)			
Median (Min, Max)			
Linus Platform Lifestyle Questionnaire			
Mean ± SD (N)	N/A		
Median (Min, Max)	N/A		

Figure #
MMSE vs. Linus Score at Visit 1

This figure will be repeated for all other individual Linus platform test scores, as well as for RBANS at Visit 1 vs. Linus (Individual Platform Test or Overall Linus Score) at Visit 1 and RBANS at Visit 2 vs. Linus (Individual Platform Test or Overall Linus Score) at Visit 2

Table # Exploratory Analysis: Test-Retest Reliability Evaluative Population			
	Visit 1	Visit 2	Difference between Visit 1 and 2 (Visit 1 – Visit 2)
RBANS			
Mean ± SD (N)			
Median (Min, Max)			
Overall Linus Score			
Mean ± SD (N)			
Median (Min, Max)			
Linus Platform Drawing Test: Pre-test			
Mean ± SD (N)			
Median (Min, Max)			
Linus Platform Drawing Test: Pathfinding			
Mean ± SD (N)			
Median (Min, Max)			
Linus Platform Drawing Test: Symbol			
Mean ± SD (N)			
Median (Min, Max)			
Linus Platform Drawing Test: Connect			
Mean ± SD (N)			
Median (Min, Max)			
Linus Platform Drawing Test: Tracing			
Mean ± SD (N)			
Median (Min, Max)			
Linus Platform Decision Making and Reaction Time Test: Simple Reaction Time			
Mean ± SD (N)			
Median (Min, Max)			
Linus Platform Decision Making and Reaction Time Test: Procedural Reaction Time			
Mean ± SD (N)			
Median (Min, Max)			
Linus Platform Decision Making and Reaction Time Test: Go/No-Go			
Mean ± SD (N)			
Median (Min, Max)			
Linus Platform Decision Making and Reaction Time Test: PHQ-9			
Mean ± SD (N)			
Median (Min, Max)			
Linus Platform Speech Elicitation Tasks: Complex Picture Description			
Mean ± SD (N)			
Median (Min, Max)			
Linus Platform Speech Elicitation Tasks: Category Naming			
Mean ± SD (N)			
Median (Min, Max)			
Linus Platform Speech Elicitation Tasks: Object Recall			
Mean ± SD (N)			
Median (Min, Max)			
Linus Platform Speech Elicitation Tasks: Sentence Reading			
Mean ± SD (N)			
Median (Min, Max)			
Linus Platform Speech Elicitation Tasks: Sustained Phonation			
Mean ± SD (N)			
Median (Min, Max)			
Linus Platform Speech Elicitation Tasks: Diadochokinetic Rate			

Mean ± SD (N)			
Median (Min, Max)			
Linus Platform Speech Elicitation Tasks: Story Recall			
Mean ± SD (N)			
Median (Min, Max)			
Linus Platform Speech Elicitation Tasks: List Learning			
Mean ± SD (N)			
Median (Min, Max)			
Linus Platform Gait and Balance Assessment			
Mean ± SD (N)			
Median (Min, Max)			

*Does not include subjects who did not meet inclusion/exclusion criteria at Visit 2

This table will be repeated for all other individual Linus platform test scores, as well as for RBANS

Figure #
Test-Retest Reliability for Linus Score

[figure not shown]

Table # Mean Score Differences of Relevant Demographic/Baseline Groups Evaluable Population	
	Mean Score Difference (96% Credible Interval)
Demographic/Baseline Group 1	
Category 1	
Category 2	
...	

The rows in this table will be repeated for all relevant baseline/demographic groups

Table # Mean/Max Prediction Interval Score Differences for Difference Composite Scores Evaluable Population		
	Mean Score Difference (96% Credible Interval)	Max 96% Prediction Interval for Score Differences
Overall Linus Score	,	
Drawing Efficiency Composite Score		
Simple and Complex Motor Composite Score		
Information Processing Composite Score		
Spatial Reasoning Composite Score		

Figure #
Extension of Non-Constant Variance Model; Linus Category Consistency
